### **8.5.3 MEWs score**

Modified early warning system score (MEW) will be assessed at Visit 1 (Day 1), Visit 6 (Day 15) and Visit 7 (Day 28). The total score is a sum of the five categorized components that will be assigned a score between 0 to 2 or 0 to 3. A higher score is worse. The components are systolic blood pressure, heart rate, respiratory rate, temperature and the alert/voice/pain/unresponsive score.

### **8.5.4 SpO2**

Resting peripheral capillary oxygen saturation (SpO2) will be measured 3 times per day. An average value across the three assessments will be calculated before the analysis of change from baseline.

### **8.5.5 PaO2/FiO2**

The ratio of partial pressure of oxygen (PaO2) and fraction of inspired oxygen (FiO2) will be calculated.

## **9 Patient disposition**

The number and percentage of patients who were enrolled, randomized, who initiated and who completed or discontinued treatment early, together with the reasons for discontinuations, will be presented by treatment group. The number of patients in the All Treated population will be presented.

## **10 Demographics and baseline characteristics**

### **10.1 Demographics and baseline characteristics**

Baseline characteristics including weight, height and oxygen levels, demographic data including age, sex, race, and ethnicity, and physical examination data, will be presented by descriptive statistics.

### **10.2 ECG and vital signs at screening**

ECG and vital signs collected at screening will be summarized with descriptive statistics.

### **10.3 Medical history**

The number and percentage of patients with medical history of particular interest will be presented separately. Other medical history will be summarized by system organ class (SOC) and preferred term (PT).

Medical history data will be coded using the latest version of Medical Dictionary for Regulatory Activities (MedDRA).

## **11 Prior and concomitant medication**

All prior and concomitant medication will be coded using the latest version of World Health Organization drug dictionary (WHO Drug).

The preferred term grouped by ATC level 4 will be used for presentation and sorted in descending order of frequency in total (the treatment groups together) at the top in the table. Prior medication, concomitant medication at randomization and onset of new concomitant medication after randomization during the study will be summarized separately.

## **12 Efficacy analyses**

### **12.1 Primary efficacy endpoint**

For the analysis of the primary endpoint, each of the two pairwise comparisons, emapalumab/anakinra versus standard of care, at both the end of Stage 1 and at the end of Stage 2, will be undertaken using Fisher's exact test comparing the proportion of patients with treatment success.

The null and alternative hypotheses with respect to the primary endpoint are defined as:

$H_0: P_{\text{treatment}} = P_{\text{SoC}}$

$H_A: P_{\text{treatment}} > P_{\text{SoC}}$

where P is the proportion of patients with treatment success as defined for the primary endpoint. The one-sided p-value from Fisher's exact test will be supplemented by the presentation of one-sided exact [Santner et al 1980] confidence intervals of the differences in proportion between emapalumab/anakinra and standard of care, with confidence coefficients of 97.5% at the end of Stage 1 and 84% at the end of Stage 2. Two-sided confidence intervals of the proportions in each group will also be presented, using the method of Clopper-Pearson [Clopper et al 1934].

The primary analysis will not adjust for the stratification factor glucocorticoid use at inclusion in order to avoid incorrect weights being attributed to any classes of the factors with few data points, particularly at Stage 1. However, a sensitivity analysis of the primary endpoint using exact logistic regression will be performed at Stage 1 and 2. This will allow for conditional testing of the treatment effect given the stratification factor. The results of the analysis will be presented in terms of model-adjusted treatment success rates for each treatment group, and p-values and confidence intervals for the odds ratio of the pairwise comparisons to the standard-of-care arm.

The individual success rate profiles will be displayed in a Swimmer plot with bars representing the time in the study and markers for whether IMV/ECMO was used at each visit. The purpose is to show onset of IMV/ECMO and how it evolves over time in relation to treatment.

The relationship between achieving treatment success/no treatment success and the change in hyperinflammatory parameters will be explored by treatment group in Box-Whisker plots with individual scatter.

## 12.2 Secondary endpoints supporting the primary objective

The secondary endpoints supporting the primary objective will not be analyzed at Stage 1.

### 12.2.1 Time to mechanical ventilation, hospital discharge and overall survival

Analysis of the time to mechanical ventilation from the point of randomization will be undertaken by plotting Kaplan-Meier curves for each of the 3 treatment groups and by pairwise comparisons (emapalumab/anakinra versus standard of care) using the log-rank test. Hazard ratios will be estimated using the Cox proportional hazards model and these will be presented together with 90% two-sided confidence intervals. Time to IMV *or* ECMO will be analyzed using the same approach.

Overall survival (time to death from the point of randomization) and time to hospital discharge (from the point of randomization) will not be analyzed at the end of Stage 2, but at the end of the follow-up period. This endpoint will be analyzed as for time to mechanical ventilation.

### **12.2.2 Change from baseline in MEWs score**

Change from baseline in MEWs score at Day 15/LOCF will be analyzed using analysis of covariance (ANCOVA) including treatment arm as a fixed factor and baseline MEWs score as a covariate. Least square mean changes per group, associated 90% two-sided CI, and p-values for the comparison vs. standard of care, will be presented.

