5.4.4.3 Rationale for stratifying the use of glucocorticoids

As glucocorticoids are one of the main first line anti-inflammatory treatments in secondary HLH, they have been suggested as one of the potential treatments for patients with severe SARS-CoV-2 infection [14]. Further to the relevance of the hyper-production of inflammatory cytokines in this infection, initial promising data have been reported with the use of IL-6 targeted therapies, namely tocilizumab, in the treatment of patients with SARS-CoV-2 infection [15]. Noteworthy, in this report all patients treated with tocilizumab also received glucocorticoids.

The use of glucocorticoids in patients with SARS-CoV-2 differs between regions and countries. Based on the experience accumulated so far in Europe, glucocorticoids have become part of standard of care for SARS-CoV-2 patients with hyperinflammation. Meanwhile, in US glucocorticoids currently seem not to be widely used in the treatment of patients with SARS-CoV-2 and hyperinflammation.

Interim WHO guidance argues against the use of glucocorticoids in the treatment of patients with SARS-CoV-2 infection [19]. This view is supported by the Infectious Diseases Society of America Guidelines on the Treatment and Management of Patients with COVID-19 [20].

Glucocorticoids are anti-inflammatory and the potential use of glucocorticoids could have an impact on biomarkers of hyper-inflammation and potentially also on the clinical outcome.

Since the use of glucocorticoids will differ between regions study patients will be stratified based on glucocorticoid treatment at randomization to ensure an equal distribution between treatment arms.

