## 4.3 Method of treatment assignment and randomization

This is a randomized, open-label study. The different treatment groups are;

Arm A: Emapalumab as add on to standard of care

Arm B: Anakinra as add on to standard of care

Arm C: Standard of care only

The sample size is 54 and the ratio between the treatment groups is 1:1:1, i.e., the same number of patients will be randomized to emapalumab, anakinra, or standard of care. Patients will be stratified based on glucocorticoid treatment at randomization to ensure an equal distribution between treatment arms. The randomization numbers are generated in blocks. Each block includes the three treatment groups per the ratio described above. An IWRS will be used for the randomization.

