## 6 Sample size determination

The study will enroll a total of 54 patients, 18 per arm according to the 1:1:1 randomization.

The sample size has been estimated based on the following assumptions:

- An overall one-sided significance level for efficacy of 0.097 (9.7%) and a power of 74% for each comparison under the assumption that the true success rates are 50% in the SoC group increasing to 80% in the emapalumab or anakinra groups.
- The study will consist of two stages. The Stage 1 interim analysis will be conducted after the accrual of at least 9 patients per treatment arm.
- There is the potential to stop for futility or for efficacy of emapalumab or anakinra (or both) at the end of Stage 1, but only the futility rule is binding and irrespective of the Stage 1 results, the study will not be stopped for efficacy but continue to accrue efficacy and safety data.

The value for the type I error has been chosen in recognition of the urgent unmet medical need to allow the identification of a signal, at least, from a statistical perspective. Having seen a statistical signal, it is then a matter of evaluating whether the observed treatment differences represent clinically relevant effects that can satisfy that unmet need. Assuming no untoward safety signal is observed and no futility stopping occurs at the Stage 1 interim, the decision may be taken to increase the sample size beyond 54 patients in order to accrue further safety and efficacy data. Details of this would be described in a protocol amendment. In case the outcome is statistically convincing, i.e. statistically significant on a 5% level in the stage 2 analysis, efficacy will be considered confirmed and the results may be used to seek regulatory approvals. The DRC will provide support in such discussions.

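### Randomisation is stratified by glucocorticoid use, but the secondary ANCOVA, log-rank and Cox analyses leave the stratum out, which costs some efficiency if the stratum is prognostic

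*SAP*

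**What the plan says.** SAP 4.3 sets the design: "Patients will be stratified based on glucocorticoid treatment at randomization to ensure an equal distribution between treatment arms". Protocol 5.4.4.3 gives the reason: glucocorticoids "could have an impact on biomarkers of hyper-inflammation and potentially also on the clinical outcome". It adds that their use differs between regions.

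SAP 12.2.2 analyses change in MEWS by ANCOVA, "including treatment arm as a fixed factor and baseline MEWs score as a covariate". SAP 12.2.3 to 12.2.5, 12.2.7 and 12.2.8 reuse that model for SpO2, oxygen supplementation, PaO2/FiO2, blood gases, the hyperinflammatory markers and all other laboratory parameters.

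SAP 12.2.1 analyses the time-to-event endpoints by "pairwise comparisons (emapalumab/anakinra versus standard of care) using the log-rank test" and continues: "Hazard ratios will be estimated using the Cox proportional hazards model and these will be presented together with 90% two-sided confidence intervals". It names no stratum or covariate.

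The primary endpoint is treated differently. SAP 12.1 leaves the Fisher test unadjusted on purpose, citing classes with few data points, above all at Stage 1. It adds an exact logistic regression conditional on the stratum as a sensitivity analysis. The secondary analyses have neither a stated reason nor an adjusted sensitivity analysis.

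**The concern.** When randomisation is balanced within strata, the arms differ less by chance than under simple randomisation. An ANCOVA without the stratum does not credit that balance: between-stratum variation stays in the residual, and the standard error is overstated. Log-rank and Cox analyses that omit a prognostic stratum lose efficiency in another way. The test becomes conservative, and the hazard ratio drifts towards 1.

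The documents give some cause to expect a stratum effect. Besides Protocol 5.4.4.3, inclusion criterion 5 sets different lymphocyte cut-offs according to recent systemic glucocorticoid use, and the differential count is a secondary endpoint. SAP 8.3 rules out centre effects, so this stratum is the only design factor that could pick up regional differences in steroid use. The primary objective covers hyperinflammation as well as pulmonary function. The primary endpoint is ventilation or ECMO only, so the hyperinflammation part rests on the marker analyses that use this ANCOVA.

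The reason given in SAP 12.1 does not carry over directly. SAP 12.2 says the secondary endpoints are not analysed at Stage 1, and one extra term in a linear model for 54 patients is a light demand.

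**Working it through.** **Inputs from the documents.** "The study will enroll a total of 54 patients, 18 per arm according to the 1:1:1 randomization" (SAP 6); 90% two-sided intervals (SAP 12.2.1, 12.2.2); success rates of 50% and 80% (SAP 6).

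**Assumptions, because the documents are silent.** The share of patients in the smaller stratum is q = 50% or 20%. The stratum shifts a continuous outcome by g = 0 to 1 residual SD, or multiplies the hazard by 1 to 4.

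**The plan's own figure.** The only stated power is 74%, for the primary endpoint. Exact enumeration of the two-stage Fisher design (9 then 18 per arm; bounds 0.025, 0.690 binding, 0.159) gives 15.3% at Stage 1 plus 58.3% at Stage 2, that is 73.6%, which agrees. No power or precision is stated for any ANCOVA, log-rank or Cox analysis, so there is nothing further to reproduce.

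**ANCOVA, by formula.** Leaving the stratum out multiplies the residual SD, and so the interval width, by √(1 + q(1−q)g²).
- q = 50%: g = 0.25 gives √1.0156 = 1.008; g = 0.5 gives √1.0625 = 1.031; g = 1 gives √1.25 = 1.118.
- q = 20%: 1.005, 1.020 and 1.077.

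The true standard error of an arm difference is about √(2/18) = 0.333 residual SD, so a 0.8 SD effect lies 0.8/0.333 = 2.4 standard errors from zero. The critical value is t(0.95; 50 df) = 1.676. Power is roughly Φ(2.4 − 1.676) = 76.6% with the stratum. At q = 50% without it:
- g = 0.25: Φ(2.4 − 1.689) = 76.1%
- g = 0.5: Φ(2.4 − 1.728) = 74.9%
- g = 1: Φ(2.4 − 1.874) = 70.1%

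**ANCOVA, by simulation** (three arms of 18, stratified permuted blocks, 4,000 runs, q = 50%, effect 0.8 SD):

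| Stratum shift (residual SD) | Width, without / with stratum | Power without | Power with |
|---|---|---|---|
| 0 | 0.999 | 75.1% | 75.2% |
| 0.25 | 1.007 | 75.3% | 75.7% |
| 0.5 | 1.031 | 73.7% | 75.3% |
| 1 | 1.123 | 67.5% | 74.4% |

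At a 1 SD shift the nominal 90% interval covers 93.8% without the stratum and 90.7% with it; the nominal 10% test has size 6.2% and 9.3%. At q = 20% the width ratios are 0.999, 1.004, 1.020 and 1.078. A further simulation gave unadjusted power of 75, 75, 74 and 69% over the same four shifts, against 75 to 76% adjusted.

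**Log-rank, by simulation** (18 versus 18, follow-up cut at Day 15, two-sided 10%, 2,500 runs). The treatment hazard ratio is the one implied by the planning rates, ln 0.8 / ln 0.5 = 0.322.

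| Stratum hazard ratio (q = 50%) | Power unstratified | Power stratified |
|---|---|---|
| 1 | 61.7% | 61.6% |
| 1.5 | 62.4% | 62.9% |
| 2 | 58.1% | 59.4% |
| 4 | 57.6% | 63.0% |

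With no treatment effect and a stratum hazard ratio of 4, the nominal 10% test has size 6.2% unstratified and 9.8% stratified. A further simulation at stratum hazard ratio 4 gave 58% against 64%.

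**Cox, same runs.** At a stratum hazard ratio of 4 and q = 50%, the mean log hazard ratio is −1.11 without the stratum, −1.22 with it as a covariate and −1.20 stratified. The interval widths on the log scale are 2.134, 2.154 and 2.160. At q = 20% the means are −1.07, −1.22 and −1.18, and the widths 2.117, 2.188 and 2.224. Across the scenarios the interval without the stratum is 0 to 5% narrower, never wider. The adjusted means overshoot the true value ln 0.322 = −1.13, and at q = 20% the unadjusted mean is also beyond it (−1.21) when the stratum has no effect. This looks like a small-sample feature, so read the gap between models rather than the distance from the truth.

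Monte Carlo error is about 0.7 points for ANCOVA power and 1 point for survival power, so the 1-point loss at stratum hazard ratio 2 is within noise. Runs in which the Cox fit did not converge (0 to 8%) were left out of the Cox figures.

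**The case against.** Much of the case against stands.

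- **Exploratory status.** Protocol 7.3.1 says secondary endpoints are evaluated descriptively and their p-values read as exploratory. No decision rule uses them and no power is claimed for them.
- **Direction of the error.** It is conservative. The ANCOVA estimate is not biased and false positives are not inflated.
- **Unknown strength.** Protocol 5.4.4.3 says only that an effect is possible. Neither its size nor the stratum split is given. A 1 SD shift at an even split means the stratum explains 0.25/1.25 = 20% of the variance, which is strong; a 0.25 SD shift explains 1.5% and costs almost nothing. Baseline adjustment may absorb part of any stratum effect.
- **Fewer events, smaller loss.** With an assumed 20% control event rate and treatment hazard ratio 0.4, stratified and unstratified log-rank power differed by less than 1.2 points for stratum hazard ratios from 1 to 3.
- **Sparse strata.** SAP 12.1 says the problem arises particularly, not only, at Stage 1. A lopsided split could still leave a thin stratum at Stage 2.

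These points limit the importance of the concern but do not answer it. The factor is in the design, the documents call it potentially prognostic, and no reason is given for leaving it out of these models.

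A reader might infer that all three methods give intervals that are too wide. That is a linear-model result and does not carry over to the Cox hazard ratio. A reader might also infer a large, certain loss. At a stratum hazard ratio of 6, with a one-sided 10% test and a treatment hazard ratio of 0.4, simulated log-rank power was 61% against 75%. The documents support neither that strength of stratum effect nor that test level; their 90% two-sided intervals match one-sided 5%.

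**Conclusion.** The point holds as a minor matter of efficiency. Under the assumptions above, leaving the stratum out makes the ANCOVA intervals 0 to 12% too wide and costs 0 to 7 points of power, with little effect below a shift of about 0.5 residual SD. It costs the log-rank test about 1 point at a stratum hazard ratio of 2 and 5 to 6 points at 4, and it moves the Cox estimate towards no effect without widening its interval. With no stratum effect, width and power are essentially unchanged either way.

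A reader should not infer that the trial's main conclusion is at risk. The primary Fisher test is unadjusted for a stated reason and has its own stratum-conditional sensitivity analysis. Nothing here bears on its error rate or power.

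**What to change.** In SAP 12.2.2, add glucocorticoid use at randomisation as a factor in the ANCOVA. Sections 12.2.3 to 12.2.5, 12.2.7 and 12.2.8 inherit it by reference. In SAP 12.2.1, stratify the log-rank test and the Cox model by the same factor. Keep the unstratified versions as sensitivity analyses in case a stratum turns out sparse. Bring Protocol 7.3.3.2.1 and 7.3.3.2.2 into line. If the sponsor prefers to leave the stratum out, the SAP should give a reason that applies to the Stage 2 and follow-up analyses.

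The cost is a few words and one degree of freedom in the ANCOVA. The factor must already be recorded for the stratified randomisation, so no new data are needed.

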### **12.2.3 Change from baseline in resting SpO2 and oxygen supplementation**

Change from baseline in resting SpO2 result and in amount of oxygen supplementation during treatment over time will be summarized using descriptive statistics (mean, SD, median, Q1, Q3, min and max) for each of these parameters. In addition to the change from baseline, absolute values at baseline and at each visit will be summarized.

Furthermore, change from baseline in resting SpO2 and oxygen supplementation at Day 15/LOCF will be analyzed using ANCOVA as described in 12.2.2.

### **12.2.4 Change from baseline in PaO2/FiO2**

Change from baseline (screening) during treatment by visit will be summarized using descriptive statistics as described in 12.2.3.

Furthermore, change from baseline in PaO2/FiO2 at Day 15/LOCF will be analyzed using ANCOVA as described in 12.2.2.

### **12.2.5 Change from baseline in hemogasanalysis**

Change from baseline in the hemogasanalysis parameters (pH, carbon dioxide tension (pCO2), oxygen tension (pO2), electrolytes, lactate and hemoglobin) during treatment by visit will be summarized using descriptive statistics as described in 12.2.3.

Furthermore, change from baseline in hemogasanalysis parameters at Day 15/LOCF will be analyzed using ANCOVA as described in 12.2.2.

### **12.2.6 Amelioration of the findings of high-resolution CT scan or X-ray of the chest**

Amelioration in the findings of high-resolution CT scan or X-ray of the chest will be summarized in a shift table showing the number and percentage of patients that had normal, abnormal (not clinically significant) or abnormal (clinically significant) findings at screening and at Day 15.

### **12.2.7 Change from baseline in hyperinflammatory parameters**

Change from baseline in hyperinflammatory parameters (ferritin, LDH and D-dimers) during treatment by visit until Day 15 will be summarized using descriptive statistics as described in 12.2.3.

Furthermore, change from baseline in hyperinflammatory parameters at Day 15/LOCF will be analyzed using ANCOVA as described in 12.2.2.

In addition, for each hyperinflammatory parameter, a summary will be included with the number and percentage of patients that had:

- at least 50% improvement from baseline to Day 15, *and*
- normalization by Day 15

### **12.2.8 Change from baseline in other relevant laboratory parameters**

Change from baseline in other relevant laboratory parameters during treatment by visit until Day 15 will be summarized using descriptive statistics as described in 12.2.3.

Furthermore, change from baseline in other relevant laboratory parameters at Day 15/LOCF will be analyzed using ANCOVA as described in 12.2.2.

## **12.3 Subgroup Analyses**

No formal subgroup analyses are planned.

## **12.4 Exploratory endpoints**

### **12.4.1 Clinical status assessed by a 7-point ordinal scale**

Clinical status using the 7-point ordinal scale is an exploratory endpoint and the data collected will be summarized to show the number and percentage of patients in each category over time.

### **12.4.2 Pharmacokinetics**

PK data will be listed and summarized at each visit with descriptive statistics.

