²Includes demographics, medical and surgical history and prior medication.

³Including recording of body weight and length.

⁴Body temperature, blood pressure, heart rate, respiratory rate and oxygen saturation.

⁵HRCT scan results and laboratory results already available in medical records at the time of informed consent can be used to confirm eligibility, if collected within 72 hours. ⁶Ferritin, LDH, D-dimers. WBC with differential counts, RBC, Hb, Platelet count, Fibrinogen, Complement C3/C4, Prothrombin Time, Cardiac troponin, AST, ALT, total bilirubin levels, CRP and Creatinine.

⁷Only applicable for females of childbearing potential.

⁸Emapalumab will be administered once daily Days 1, 4, 7, 10 and 13 (Section 5.4.5.1). Anakinra will be administered 4 times daily for 15 days i.e., Day 1 to 15 (Section 5.4.5.2). ⁹For details, see Section 5.4.7.

¹⁰Requirement for invasive mechanical ventilation or ECMO.

¹¹Incidence, severity, causality and outcomes of treatment-emergent serious AEs, adverse events leading to premature discontinuation of study treatment and adverse events of special interest.

¹² PD biomarkers: CXCL9, IFNy, IL-1, IL-6, sIL-2R. Samples to be collected Visit 1:pre-dose and thereafter at Visits 2, 3, 4, 5 and 6: end of infusion. (for anakinra treated patients; samples will only be collected in connection with the first infusion per day) In addition, at Visits 8 and 9, a PD biomarker sample will be collected in case the patient is coming to the clinic for these visits.

¹³Local TB testing to confirm patient status. Test result are accepted post randomization not to delay treatment.

Confidential

Page 34 of 62

Version 7.0 Final Protocol, Date 24 Jun 2020

Sobi

Emapalumab/Anakinra

Emapalumab/Anakinra

¹⁴Local PCR testing to confirm patient SARS-CoV-2 diagnosis. For sites where PCR is not part of hospital routine for confirming diagnosis/eligibility, test results are accepted post randomization not to delay treatment.

¹⁵ PK blood samples will be collected at Visit 1: pre-dose and at end-of infusion (for anakinra after the first infusion per day), and thereafter at Visits 2, 3, 4, 5 and 6: at end-of infusion (for anakinra treated patients; samples will only be collected in connection with the first infusion). In addition, for emapalumab treated patients at Visits 7. For Visit, 8 and Visit 9, a PK sample will be collected in case the patient is coming to the clinic for these visits.

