5.5.5.2 Pharmacokinetics

PK blood samples will be collected for all patients receiving active study treatment. At Visit 1 sampling should be done pre-dose and at end-of infusion and during Visits 2, 3, 4, 5 and 6 a PK sample should be taken at end-of infusion. For anakinra treated patients; samples will only be collected in connection with the first infusion per day. In addition, for emapalumab treated patients, a PK sample will be collected also at Visit 7 (Day 28) and during follow-up on Visit 8 and 9 in case the patient is at the clinic for these visits. It should be noted that a separate iv line will have to be used when collecting the PK samples, ie not the same iv line as used for the iv infusion of active study treatment.

The date and time of blood sampling will be recorded in the CRF. Samples will be sent to a central laboratory for analysis.

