### **3.3 Exploratory objectives**

An exploratory objective of this study is to evaluate the clinical status based on a 7-point ordinal scale.

An exploratory objective of this study is to evaluate the PK of emapalumab and anakinra.

An exploratory objective of this study is to assess the effect of anakinra and emapalumab on CXCL9, IL-1, IL-6, sIL-2R and selected biomarkers relevant for hyperinflammation, whenever possible.

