## 8.1 Time windows

For the purpose of the statistical analysis and if not otherwise specified, all the variables (primary, secondary and exploratory variables) will be assigned to the visit/assessment timepoint in which they were collected depending on the following analysis time windows in Table 1.

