**Table 2 Time windows**

Visit	Study Day	Study Day window
1	1 (Baseline)	≤1
2	4	2-5
3	7	6-8
4	10	9-11
5	13	12-14
6	15	15-16
7	28	Early follow-up
7/TC	Week 6	Only follow-up of survival and hospital discharge and continued AE reporting in accordance with the protocol.
8/TC	Week 10	

Unscheduled visit data will be considered when assigning assessments to the analysis visit. If more than one assessment of the variable (scheduled or unscheduled) falls in the same time window but on different days, the closest to the scheduled visit day will be taken, or the earlier, in the event the values are equidistant from the nominal visit date. If several measurements are collected during the selected day, the average (for numeric values)/worst (for categorical values) of the measurements will be taken.

In summaries of extreme values as opposed to visit-based summaries, all post baseline values collected are used including those collected at unscheduled visits regardless if the value is closest to the scheduled visit date or not. For summaries at a patient level, all values should be included, regardless of whether they appear in a corresponding visit-based summary, when deriving a patient level statistic such as a maximum.

Listings will display all values contributing to a time point for a patient.

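### Read as written, the SAP averages the pre-dose and end-of-infusion samples in the Visit 1 row of the exploratory PK table

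*SAP*

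**What the plan says.** PK is exploratory. SAP 3.3 states: "An exploratory objective of this study is to evaluate the PK of emapalumab and anakinra". The analysis text, SAP 12.4.2, is a single sentence: "PK data will be listed and summarized at each visit with descriptive statistics". Protocol 7.3.5 says no more than this.

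SAP 8.1 sets the general visit rule. Unless something else is stated, "all the variables (primary, secondary and exploratory variables) will be assigned to the visit/assessment timepoint in which they were collected", using the windows in SAP Table 2, which has one row per visit. Below that table comes the same-day rule: "If several measurements are collected during the selected day, the average (for numeric values)/worst (for categorical values) of the measurements will be taken". SAP 12.4.2 makes no exception to it.

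The sampling plan is in Protocol 5.5.5.2. For the first visit, "At Visit 1 sampling should be done pre-dose and at end-of infusion". After that, "during Visits 2, 3, 4, 5 and 6 a PK sample should be taken at end-of infusion". Footnote 15 of the Protocol's schedule of events gives the same plan. For anakinra, the samples belong to the first infusion of the day.

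Two further places matter. SAP section 1 defines baseline as the state before study drug on Day 1, and SAP Table 2 labels Visit 1 as baseline. SAP 3.4.4 also names PK parameters from non-compartmental and population analysis, where applicable.

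**The concern.** Visit 1 is the only visit with two planned PK samples on one day, and they measure different things: the level before any study drug and the level just after the first infusion. Their average estimates neither. The general rule nevertheless calls for it, and the averaged value would stand in the same column as plain end-of-infusion values from later visits. A reader of that table would underestimate exposure after the first dose and could take the rise from Visit 1 to later visits for accumulation.

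At stake is the usefulness of one exploratory table. The first-dose level is the natural reference for the later rows, and SAP section 2 says the planned analyses may go into regulatory submissions or manuscripts.

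**Working it through.** The documents give no PK concentration, peak or accumulation figure, so there is no plan figure to reproduce. The check is direct arithmetic on the stated rules.

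**Inputs**
- Visit 1: two samples on Day 1, pre-dose and end of infusion (Protocol 5.5.5.2).
- Visits 2 to 5: one sample each, at end of infusion, so nothing to average (same section).
- Numeric same-day values are averaged (SAP 8.1, text below Table 2).
- Anakinra: 100 mg per infusion throughout (Protocol 5.4.5.2).
- Emapalumab: 6 mg/kg on Day 1, then 3 mg/kg on Days 4, 7, 10 and 13 (Protocol 5.4.5.1).
- Pre-dose level: not given. It is written as a fraction f of the end-of-infusion level C, with f = 0 as the main assumption and a range shown.
- Handling of values below the quantification limit: not stated in either document.

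**Visit 1 row under the averaging rule**

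Visit 1 value = (fC + C)/2 = C(1 + f)/2. Any ratio of a later visit to Visit 1 is therefore multiplied by 2/(1 + f).

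| Pre-dose level | Visit 1 value / C | Multiplier on later-visit ratios |
|---|---|---|
| f = 0 (below-limit counted as 0) | 0.50 | 2.00 |
| f = 0.01 | 0.505 | 1.98 |
| f = 0.05 | 0.525 | 1.90 |
| f = 0.10 | 0.55 | 1.82 |
| Below-limit set to missing | 1.00 | 1.00 |

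If 2 of 18 patients lack a pre-dose value and the rest have 0, with similar end-of-infusion levels in both groups, the mean Visit 1 factor is (16 × 0.5 + 2 × 1)/18 = 0.556 and the multiplier is 1/0.556 = 1.80. Where every patient has f = 0, each Visit 1 value is halved, so the mean, median and SD are halved too.

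**What a reader would see, with f = 0**

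*Anakinra.* The dose per infusion is constant. A true later-to-first ratio of 1.0 would appear as 2.0.

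*Emapalumab.* Let r be the fraction of the Day 1 end-of-infusion level still present on Day 4. The documents do not give r. Assume linear kinetics and comparable infusions. The true Visit 2 / Visit 1 ratio is (6r + 3)/6 = 0.5 + r, and the tabulated ratio is (6r + 3)/3 = 1 + 2r.

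| r (assumed) | True ratio | Tabulated ratio |
|---|---|---|
| 0.25 | 0.75 | 1.50 |
| 0.50 | 1.00 | 2.00 |
| 0.75 | 1.25 | 2.50 |
| 0.90 | 1.40 | 2.80 |

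Even the true ratio is not a measure of accumulation, because the dose differs between the two visits.

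**The alternative reading**

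If Visit 1 means baseline, and baseline means before study drug, the Visit 1 row holds the pre-dose value only. Nothing is averaged, but the end-of-infusion sample from the first dose then has no row.

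**A related mismatch at Visit 6**

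Visit 6 is Day 15, with a window of ±1 day (Protocol 5.5.1.5). Protocol 5.5.5.2 describes its PK sample as end of infusion for patients on active treatment generally. Anakinra is infused through Day 15. The last scheduled emapalumab infusion is on Day 13, so for that arm the sample description and the dosing schedule do not agree.

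**The case against.** The strongest reply is that averaging is only one reading. SAP 8.1 speaks of a visit or an assessment timepoint, and pre-dose and end of infusion are distinct planned timepoints. The same-day rule sits in a paragraph that opens with unscheduled data. SAP 8.5.4 separately prescribes averaging the three daily SpO₂ values, which would hardly be needed if 8.1 already averaged every planned same-day measurement. This has weight: averaging is not certain to be what gets programmed. It does not remove the problem. The same-day sentence is not limited to unscheduled values, SAP Table 2 offers one slot per visit, and SAP 12.4.2 names no sampling times. The baseline reading drops the first-dose level altogether, so both readings need the same clarification.

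A second reply is that the harm is small, and this stands. A reader might infer that the visit summary is the only PK analysis in the SAP and that first-dose exposure would be lost. The documents do not support that: SAP 3.4.4 names non-compartmental and population PK, which can use the individual samples, Protocol 5.5.5.2 has sampling times recorded, and SAP 8.1 keeps all contributing values in the listings. SAP section 12 gives no method for those PK parameters, but they are planned where applicable.

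A third reply is that exact halving depends on an unstated rule. That also stands: with below-limit pre-dose values set to missing, the averaging has no effect where the pre-dose value is below the limit.

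**Conclusion.** The point holds as a minor one. As written, the SAP does not define the Visit 1 row of the PK table properly: the row either averages two samples of different kinds or leaves out the first-dose end-of-infusion level. Under averaging, the row is 0.50 of the end-of-infusion level if below-limit pre-dose values count as 0, 0.55 if the pre-dose level is 10% of it, and 1.00 if below-limit values are set to missing. Ratios of later visits to Visit 1 would be inflated by a factor between 1.00 and 2.00 accordingly.

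Two stronger inferences should be resisted. One is that the plan doubles accumulation: neither document plans an accumulation ratio or any comparison with Visit 1, so the inflation exists only for someone who forms that ratio from the table. The other is that the larger first emapalumab dose vanishes from the results. That would require pre-dose zeros, linear kinetics and comparable infusions. Protocol 5.4.5.1 lets infusion time vary from 1 to 2 hours with volume, and the individual data remain available in any case.

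No efficacy, safety or interim decision in the documents uses this table.

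**What to change.** In SAP 12.4.2, state that:

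- PK concentrations are summarised by nominal sampling time, with Visit 1 pre-dose and Visit 1 end of infusion as separate rows and each later visit labelled by the sample actually scheduled for that arm;
- the same-day averaging of SAP 8.1 does not apply to PK;
- values below the quantification limit are handled by a named rule.

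For emapalumab, the sponsor should reconcile the Visit 6 (Day 15) sample description in Protocol 5.5.5.2 and footnote 15 of the schedule of events with the dosing schedule, whose last infusion is on Day 13. Until that is done, the table should not label this sample as end of infusion.

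The cost is a few sentences in the SAP, one more table row and a wording check in the Protocol. No new data are needed.
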